5.11 Clinical Trials

Propranolol (Inderal®) is manufactured by Wagner Pharmaceuticals Inc. and Apotex Pty Ltd and is supplied as a prescription-only medicine available through pharmacies. INDERAL tablets are available in 10 mg and 40 mg doses of propranolol hydrochloride, intended for oral administration. Propranolol is listed on the Australian Register of Therapeutic Goods (ARTG) as a therapeutic substance. We will be seeking approval from the TGA for use of propranolol 'off label' in the clinical trial under the supervision of the study physician (GP).

Approved therapeutic indications

Approved therapeutic indications include:

- Angina pectoris
- Hypertension
- Prevention of migraine
- Cardiac dysrhythmias: for treating specific intrinsic cardiac dysrhythmias, dysrhythmias associated with thyrotoxicosis, anxiety-induced tachycardia, and certain drug-induced dysrhythmias, such as tachycardia caused by digitalis or adrenaline overdose.
- Essential tremor, including familial and senile tremor
- Pheochromocytoma (to be used only with concurrent α -receptor blockade)
- Hypertrophic subaortic stenosis
- Suspected or definite myocardial infarction
- Fallot's tetralogy

Mechanism of action

Propranolol hydrochloride is a β -adrenoreceptor blocking agent that acts non-selectively on both β_1 and β_2 receptors. It has minimal intrinsic sympathomimetic activity and exhibits some membrane-stabilizing properties. Inderal is a racemic mixture, with the S(-) isomer being the active form of propranolol. The primary effect of propranolol hydrochloride is to diminish the impact of excessive sympathetic nervous stimulation on the heart, leading to a reduction in pulse rate, cardiac contraction force, and cardiac output. This, in turn, significantly decreases myocardial oxygen demand, to a greater extent than the reduction in workload. These combined effects offer therapeutic value in the treatment of several cardiovascular conditions.

The mechanism by which propranolol hydrochloride lowers elevated blood pressure remains unknown. However, the drug has been shown to inhibit exercise-induced tachycardia, with this effect being directly related to its plasma concentration. Notably, no correlation has been established between the plasma concentration of propranolol and its antihypertensive effects.

The anti-anginal activity of propranolol hydrochloride likely stems from a reduction in left ventricular work and oxygen utilization due to the inhibition of cardiac sympathetic nerve stimulation. Propranolol hydrochloride has also demonstrated serotonin antagonism, though the therapeutic benefit of this property in centrally mediated disorders is still uncertain. As with other β -adrenoreceptor blocking agents, propranolol hydrochloride has negative inotropic effects, and therefore, it is contraindicated in patients with congestive heart failure.

Known adverse events

Propranolol hydrochloride is usually well tolerated, and side effects are transient in nature, rarely necessitating withdrawal of treatment. The most serious adverse reactions encountered are congestive heart failure and bronchospasm in susceptible patients. Common adverse reactions include fatigue and/or lassitude (often transient), bradycardia, cold extremities and exacerbation of Raynaud's phenomenon, sleep disturbances including vivid dreams/nightmares. Other less frequently reported adverse reactions include gastrointestinal disturbances (nausea, vomiting, diarrhoea, abdominal pain), congestive heart failure, dizziness, bronchospasm. Rare cases of thrombocytopenia and purpura have been reported. CNS symptoms including mood changes and hallucinations have been reported rarely. It should be noted that those symptoms have been reported among individuals taking propranolol every day for prolonged periods of time. Our study participants will be taking propranolol once a week, for 6 weeks.

Known contraindications or warnings:

- **Cardiovascular:**
 - o Congestive heart failure
 - o Right ventricular failure secondary to pulmonary hypertension
 - o Significant right ventricular hypertrophy
 - o Sick sinus syndrome
 - o Sinus bradycardia (less than 45 to 50 beats/minute)
 - o Second- and third-degree A-V block
 - o Hypotension
 - o Severe peripheral arterial circulatory disturbances
 - o Prinzmetal's angina
- **Hypoglycaemia, prolonged fasting and metabolic acidosis:**
 - o Propranolol must not be used in patients prone to hypoglycaemia, i.e. patients after prolonged fasting or patients with restricted counter regulatory reserves. In metabolic acidosis (e.g., in diabetes), the premonitory signs of hypoglycaemia may be masked in patients receiving hypoglycaemic agents.
- **Asthma/bronchospasm:**
 - o β -adrenergic blockade of the smooth muscle of bronchi and bronchioles may result in an increased airways resistance. These drugs also reduce the effectiveness of asthma treatment. This may be dangerous in susceptible patients. Therefore β -blockers are contraindicated in any patient with a history of bronchial asthma, airways obstruction or a tendency to bronchospasm. Use of

cardioselective β -blockers can also result in severe bronchospasm. If such therapy must be used, great caution should be exercised. Alternative therapy should be considered.

- **Other:**
 - o Allergic disorders (including allergic rhinitis) which may suggest a predisposition to asthma or bronchospasm
 - o Shock (including cardiogenic and hypovolaemic shock)
 - o Hypersensitivity to the drug
 - o Anaesthesia with agents that produce myocardial depression (e.g., ether, chloroform)
 - o Untreated pheochromocytoma

Pharmacokinetics

- o **Absorption:** Studies with propranolol hydrochloride in humans indicate that it is almost completely absorbed from the intestine. A large part of the absorbed drug is lost to systemic circulation due to the first pass metabolism in the liver. After repeated administration, the first pass removal process becomes saturated and, at steady state, the plasma concentration is proportional to the dose, although there is some variation between patients as to the blood levels achieved at a given dose. In addition, correlation of plasma level to therapeutic effect varies considerably with propranolol as with some other β -blockers. Blood level measurements show that after intravenous administration, the concentration in the circulation decreases rapidly due mainly to uptake by tissues generally.
- o **Bioavailability:** In general, the peak blood level occurs between 1 and 3 hours after oral administration and will have an average value of 0.1 $\mu\text{g}/\text{mL}$ per 80 mg single dose. The peak blood level is proportional to the dose. With chronic administration the mean plasma half-life is from 3 to 6 hours, determined by clearance and plasma binding. Following intravenous administration, the plasma half-life of propranolol is about 2 hours and the ratio of metabolites to parent drug in the blood is lower than after oral administration. In particular 4-hydroxypropranolol is not present after intravenous administration.
- o **Distribution:** Propranolol is absorbed from the circulation and is widely distributed throughout the body tissues.
- o **Protein binding:** Approximately 93% is plasma bound in humans.
- o **Metabolism:** Propranolol is completely metabolised, primarily by the liver. Hydroxylation of the aromatic nucleus occurs with degradation of the isoprenaline side chain. Over 20 metabolites have been identified. One of these, the 4-hydroxy metabolite, found only after oral administration has β -adrenergic blocking properties.
- o **Excretion:** Some 95 to 100% of a dose of propranolol hydrochloride is excreted as metabolites and their conjugates in the urine.
- o **Half-life:** The plasma half-life of oral propranolol is of the order of 3 to 6 hours. The pharmacological effect lasts much longer.

Please see Appendix G for interactions with other medicines and special warnings.

6. Results, Outcomes and Future Plans

At the time of submission, the project timeline estimates that participant data collection will be completed by the end of 2027. At the close of data collection, all data will be entered and saved on secure TI/NPRC servers, accessible only to the PI and authorised research members. All research staff involved in data collection and/or management who subsequently leave the research study will have access to all electronic data revoked.

Disseminating general study findings to the participants and their families is of a high priority. Our participants will be given the option to receive general results from the study by requesting these from their referring medical officer. This will assist the patients in the future if they want to use this treatment option as part of their management; it also allows their participation, commitment, and contribution to literature and science to be acknowledged and valued. Individual results will not be available to participants and UniSC retains ownership of all data produced as a result of this research.

Data generated from this research will be published in relevant academic journal articles, both as part of PhD student's thesis and research output of post-doctoral researchers at the Thompson Institute. The findings of this report will be readily accessible to staff and students at the TI/NPRC.

All publications and presentations will only report aggregate de-identified data, with no identifiable information published at any point. We expect this study will receive widespread public interest and media attention, enabling public dissemination of findings. There are no anticipated restrictions on publication of results from this research. We are open to share the information and key implications with the community, relevant authorities, local clinical organisations, and other stakeholders to realise the potential benefit of results with the wider community, and on international grounds, especially for sufferers, their families, and carers. In that respect, we will also ensure participant confidentiality and protect the intellectual property rights of the TI/NPRC.

To the extent allowed by the conditions of ethical approval, participant consent, funding, and legislative stipulations, we are open to sharing information relating to study design, resources and results with research entities and/or psychiatric/psychological practices which request access. If information is shared, all data and results will remain de-identified and only the data of those participants who consented to the sharing of their data will be included. Participants are informed of all planned sharing and future data use in the PICF. By signing this form, they are indicating this has been explained to them and that they understand.

7. Appendix

7.3 Appendix C. Visual flow of participant journey

Participant journey – PTSD Research Clinic

7.4 Appendix D. Medical assessment

Measures	Protocol and Key Questions

Example physical health assessment questions
	
Study physician will perform a full physical examination including, but not limited to: Neurological system, cardiovascular system, Respiratory system, gastrointestinal system
 
A 12-lead ECG will be performed
 
Lying and standing blood pressure, as an active standing test
 
 • Participant is to be placed in a supine position, • Lying blood pressure is to be taken after being positioned supine for at least 5 minutes • The participant is to transition to a standing position • Standing blood pressure is to be taken immediately, then after 1 minute of standing. 
A participant will be excluded if there is a reduction in systolic blood pressure by ≥ 20 mmHg; a reduction in diastolic blood pressure by ≥ 10 mmHg or a heart rate increase of ≥ 30 beats per minute
 
Heart rate variability using ECG rhythm strips.
 
Drug and alcohol screen
 
Significant medical history, past or present, including diagnosis, prognosis, and severity
 
Medication the participant has taken in the last 3 months, including current regular medications:
 
 • Name: • Dosage: • Units: • Start date: • End date: • Use: 
Basal systolic blood pressure (exclude if < 100 mm Hg)
 
Basal heart rate (exclude if < 50 bpm)
 
History of adverse reaction to a beta-blocker in the past (exclude if YES)
 
Currently using a drug/substance that can interact adversely with propranolol? (exclude if YES)
 
If this person pregnant or breastfeeding a child? (exclude if YES)
 
Is this participant using contraceptives? (YES/NO/N/A)
 
If yes, what type:
 
Does this person present with a medical contraindication to take propranolol (exclude if YES):
 
 • Chronic obstructive asthma and bronchopneumopathy • Uncontrolled heart failure • Cardiogenic shock • Second- and third-degree atrioventricular block not paired • Spastic angina • Unpaired ear sinus disease • Bradycardia • Raynaud's syndrome and peripheral arterial disorders • Untreated pheochromocytoma • Arterial hypotension • Hypersensitivity to propranolol • Antecedent anaphylactic reaction • Hypoglycemia predisposition • Orthostatic hypotension • Other: 
Taking this all into account, can this person receive propranolol? (YES/NO)
 
Dosage and prescription of propranolol
 
Participants height:
 
Determine the dosage using the table below:


Size (cm) Men	Size (cm) Women	Recommended dosage/propranolol session	Tablet (40mg)	Total number of tablets required
-	<1m55	40mg	1	8
<1m55	<1m65	50mg	1 ¼	10
<1m65	<1m75	60mg	1 ½	12
<1m75	<1m85	70mg	1 ¾	14
<1m85		80mg	2	16

Prescribe oral propranolol tables as per recommended dosage

- The number of pills is based on weekly treatment of 6 weeks
- Dosage should be taken with food 60min before the session

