5.1 Methodological Approach

In this study, participants will receive manualised (Brunet & Lonergan, 2010) propranolol-based reconsolidation blockade treatment (hereafter called RT) once per week for six weeks in a single treatment arm. Each RT session will be conducted by trained practitioners. Session 1 will last 50 minutes while Sessions 2-6 will last 25 minutes and involve a script recall exercise to activate the specific trauma memory targeted for that session. Participants will be instructed to take the study oral medication (1mg/kg according to ideal weight) 60 minutes with a light snack before each scheduled RT session (i.e., 6 once-a-week doses over 6 weeks). The first dose will be taken on site under supervision of a registered nurse with access to a medical doctor. Subsequent doses will be taken at home before each treatment session. On the day of the first propranolol administration, the research trials

physician (GP) will be on-site to monitor for potential hypotensive events and ensure participant safety. This protocol builds on previous propranolol research and aligns with memory reconsolidation theory principles.

Throughout the study, participants will remain under the care of their existing treating team (i.e. medical practitioner, psychiatrist and/or psychologist), who will oversee any modifications to their existing treatments. RT will be used as an adjunctive treatment, allowing participants to maintain their current psychotropic medications, if any, under their physician's guidance. Any changes in medication will be documented by the study staff. It will be strongly recommended to participants and their treating team to not commence any new mental health treatments during the clinical study.

The primary outcome of the study is a change in PTSD symptomatology, assessed using the battery of psychological assessments (i.e., PCL-5, structured clinical interview) at several time points:

- T1 Baseline assessment (week 0)
- T3 post-treatment assessment (week 7 or 8)
- T5 Follow-up 2 (3 month)

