Prior to consent, participants are informed within the RPIS and PICF (Appendix A and B), that their MRI brain scan is being conducted for research purposes, and as such, is not clinically valid for diagnosis. Importantly, participants are also informed that our research team is not qualified to provide clinical opinions or medical diagnosis based on their brain scans, and reviewing their scans for that purpose is not within our team's scope of practice. However, if a suspected incidental finding or abnormality is identified by our research team or scan operators, we will adhere to the incidental finding policy indicated within the Working with MRI Guideline. Participants are also given the choice to indicate if they would like to be informed of an incidental finding, should one be identified. In short, if a senior research staff involved in the MRI procedure identifies a suspected incidental abnormality, and participants have consented to being notified of this occurrence, this will be communicated to the participant via a phone call from either the principal investigator or a senior member of the clinical research unit. This is the approved policy put forth by the MRI Operations and Safety committee. Participants will be offered a letter addressed to their GP, with a photo of the scan, and may choose to meet with their GP of their own accord. Participants are informed in the PICF, and again in-person, that the MRI scan is not a medical scan, and that research staff are not qualified to make any diagnoses.

Intervention phase (weeks 1 – 6)

Provided that no contraindications to participation were identified in the T1 or T2 assessments, participants will take part in a 6-week treatment period, consisting of once per week RT sessions. If participants miss more than 3 weeks of RT intervention, they will be excluded from the study. Each RT session will last between 25 and 50 minutes per session. Participants will be on their "treatment as usual" regimen which implies that they will continue to take all their regular medications. The propranolol medication used to conduct RT will be adjunctive (as approved by the study GP regarding possible contraindications). Following each treatment session, participants will provide a saliva sample through passive drool collection.

Post-treatment assessment (T3) (week 7 or 8)

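### The Appendix D prescribing table totals tablets for eight doses in every row, although its own note and the protocol's dosing schedule give six weekly doses

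*Protocol*

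**What the plan says.** Appendix D tells the study physician "Determine the dosage using the table below". The table that follows sets, by sex and height, a dose per session from 40 to 80 mg, the number of 40 mg tablets that makes up that dose, and a column headed "Total number of tablets required". Beneath it stand the instruction "Prescribe oral propranolol tables as per recommended dosage" and the note "The number of pills is based on weekly treatment of 6 weeks".

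The body of the protocol describes the course as follows:

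- Section 5.1 has one dose before each treatment session, "i.e., 6 once-a-week doses over 6 weeks".
- Section 5.4, Intervention phase, says that "participants will take part in a 6-week treatment period, consisting of once per week RT sessions".
- Section 5.11, under known adverse events, says: "Our study participants will be taking propranolol once a week, for 6 weeks".

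On where the doses are taken, section 5.1 says "The first dose will be taken on site under supervision of a registered nurse". The later ones are taken at home before each session.

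**The concern.** The totals column and the note that explains it give different numbers of doses. The note ties the count to six weekly treatments, which is the course described everywhere else in the protocol. The printed totals are larger than six times the session dose in every row.

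This would be trivial in background text. Here it sits in the table from which the prescription is written, and it is the protocol's only statement of how many tablets to supply. A participant given the full printed total would hold surplus propranolol at home after finishing the course. The return provision in the risk register (Appendix L, RC_11) covers only unused product still on site at the end of the trial. Anyone reconciling tablets against the table would also find totals that six doses cannot account for.

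**Working it through.** **Inputs.** Dose per session, tablets per session and total tablets come from the Appendix D table. The number of doses, six, comes from the table's note and from sections 5.1 and 5.11. Section 5.4 counts weekly sessions rather than doses, but with section 5.1's one dose per session it leads to the same six.

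**Step 1: are the session doses consistent?** Tablets × 40 mg = 40, 50, 60, 70 and 80 mg, which matches the table in every row. The per-session columns are sound, and the rows have come through intact.

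**Step 2: how many doses do the printed totals supply?** Implied doses = total ÷ tablets per session.

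**Step 3: what do six doses need?** Tablets needed = 6 × tablets per session.

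| Dose | Tablets per session | Printed total | Implied doses | Six doses, exact | Six doses, rounded up to whole tablets |
|---|---|---|---|---|---|
| 40 mg | 1 | 8 | 8/1 = 8 | 6 | 6 |
| 50 mg | 1.25 | 10 | 10/1.25 = 8 | 7.5 | 8 |
| 60 mg | 1.5 | 12 | 12/1.5 = 8 | 9 | 9 |
| 70 mg | 1.75 | 14 | 14/1.75 = 8 | 10.5 | 11 |
| 80 mg | 2 | 16 | 16/2 = 8 | 12 | 12 |

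**Step 4: can another rule reproduce the column?**

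- Six doses, each rounded up to whole tablets: 6, 12, 12, 12, 12. This agrees in the 60 mg row only.
- Six doses, each rounded up to half tablets: 6, 9, 9, 12, 12. No row agrees.
- Seven doses: 7, 8.75, 10.5, 12.25, 14. No row agrees.
- Eight doses: 8, 10, 12, 14, 16. All five rows agree exactly.

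Tablet splitting is ruled out directly by the 40 mg and 80 mg rows, which use whole tablets and still show 8 against 6 and 16 against 12. The supervised first dose does not help either, since it could only reduce the number needed for home use.

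**Step 5: size of the surplus.**

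- Against six exact doses: 2, 2.5, 3, 3.5 and 4 tablets, or 80, 100, 120, 140 and 160 mg. That is two doses, 2/6 = 33%, in every row.
- Against whole-tablet totals: 2, 2, 3, 3 and 4 tablets, or 80, 80, 120, 120 and 160 mg. As a share, 2/6, 2/8, 3/9, 3/11 and 4/12 = 33%, 25%, 33%, 27% and 33%. In doses, 2/1, 2/1.25, 3/1.5, 3/1.75 and 4/2 = 2, 1.6, 2, 1.7 and 2.

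**The case against.** The best defence is that the totals include a deliberate margin. A constant factor of eight, even in the quarter-tablet rows, looks like a uniform rule rather than five separate slips, and a note saying the count is based on a six-week course does not strictly say that it equals six doses. Spares would also be practical. Doses after the first are taken at home an hour before the session, so a session that falls through after the tablet has been swallowed would need another dose. Up to three weeks may be missed before discontinuation (sections 5.4 and 5.5). The risk register (Appendix L, RC_10) rates late or missed attendance as likely, although it is written for assessments. Quarter tablets can break. Finally, Appendix D labels its contents as examples, and nothing tells a participant to take more than one dose a week.

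Much of this is fair as far as it goes. A two-dose reserve is plausible, and the document cannot show which was intended. But no section mentions a spare, replacement or make-up dose, the column is headed as tablets required, and the note names six weeks as its only basis. If a reserve was meant, the note omits it, and the reader still cannot derive the totals from what is written. The example label carries little weight beside explicit directions to determine the dose and prescribe from the table.

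**Conclusion.** The point holds. The printed totals supply exactly eight doses in every row, while the note and the rest of the protocol account for six. The excess is two doses, 80 to 160 mg per participant, or 1.6 to 2 doses if the six-dose totals are rounded up to whole tablets. These are maxima, reached only if the full printed total is dispensed and all six sessions are completed.

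The mismatch is certain. Whether the totals or the note should change depends on the sponsor's intention. The severity is minor: the dose per session and the one-dose-per-weekly-session schedule are consistent throughout, and nothing in the outcome, the sample size or the analysis depends on the tablet count.

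**What to change.** The sponsor should decide which was meant and make one of two changes in Appendix D:

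- **No reserve intended:** replace the totals with 6, 7.5, 9, 10.5 and 12 tablets. If only whole tablets are dispensed, use 6, 8, 9, 11 and 12.
- **Reserve intended:** keep 8, 10, 12, 14 and 16, and reword the note to say that the count covers six weekly doses plus two spare doses. It would help to add a line on returning unused tablets held at home.

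The cost is five numbers in one table, or one line of its note, in the next protocol amendment.
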